Level Up! Adaptive Gaming for Children with Upper Limb Differences

NCT Number: TBD

[name] and [name]
7-18-2023
Version 2

Level Up! Adaptive Gaming for Children with Upper Limb Differences – Study Protocol

Play is an important part of childhood development [1], and it is fair to say that leisure, fun, and entertainment are all essential aspects of life. The ICF defines participation as the nature and extent of a person's involvement in life situations [2]. Participation is essential to a child's health, well being, and development, and is often the ultimate goal of pediatric rehabilitation [3]. All individuals should have the ability to participate in their choice of leisure activities [4].

Video games are a popular form of leisure and entertainment [4], especially among children and adolescents [5]. Video games encourage participation, increase motivation to complete goals, offer rewards and immediate punishments, and have adjustable difficulties to match skill level [4]. They also foster competitiveness, cooperation, immersion, sense of control, achievement of goals, and satisfaction [4]. Not only can video games be used for entertainment, but they can also be used in a more serious context, such as in education or rehabilitation [4]. Some of their uses include increasing strength and coordination, developing a sense of autonomy, increasing self confidence, and developing the ability to learn from error [4]. There are also genre specific benefits for different types of games. Some types of games promote problem solving skills and creativity. Other types of games promote healthy, optimistic motivational styles that can be seen reflected in other aspects of life, such as school or work. Other types still can foster improved mood, increased relaxation, and decreased anxiety [6]. Creating socially inclusive games and adapting game play to promote accessibility are necessary to support all children and youth in play.

For children with an amputation or upper limb difference, full participation in playing video games is not always possible. Most mainstream video games and video game controllers require bimanual dexterity and multiple degrees of freedom in both hands to be able to operate all functions. For a child missing part or all of their hand or arm, it can be difficult to access all aspects of a controller.

Current methods of video game adaptation often involve a change to the controller or game that reduces the amount of interaction the user has with the game [4]. These methods provide incomplete accessibility which can decrease the benefits of playing video games. For example, games that have been modified or designed with the intent to make the interaction simpler may result in less demands on strength, coordination, immersion, etc., meaning less benefits to be realized in these areas. The cost associated with adapting games or controllers may also be a barrier to their use. Adapted controllers also make it more difficult for users to play with others using a standard controller because controllers cannot be shared between players and the adaptive controller may have different requirements. Given that 70% of people who play video games play with others [6], the ability to participate with others is an incredibly important factor to participation.

Providing children with an upper limb amputation or difference with the ability to play any video game with a standard controller increase their ability to participate in a main-stream childhood experience. At RCC, we have developed a video game controller adapter that allows for one-handed play. It is easily attached and removed to a standard Xbox controller, which allows inclusive play between children with and without an upper limb amputation or difference. We propose that this new technology will increase both video game performance and satisfaction, allowing children with an upper limb amputation or limb difference to realize all of the benefits of playing video games with ease. We hope that this will ultimately improve quality of life for this population.

Research Purpose

The aim of this research study is to explore whether a novel video game controller adapter designed at RCC can increase performance and/or user satisfaction while playing video games, in users with unilateral upper limb differences. This case series will use mixed quantitative and qualitative methods to compare performance and user satisfaction with and without the RCC designed video game controller adapter. We will assess performance using a standard Minecraft course for all participants. Satisfaction of the adapter will be assessed with a semi-structured interview and a Visual Analog Scale (VAS) for satisfaction, and the Quebec User Evaluation of Satisfaction with assistive Technology (QUEST) outcome measure to compare play with and without the adapter for each participant.

Research Methods

Participants & Sampling Technique: Participants will be selected through convenience sampling at the Rehabilitation Centre for Children in Winnipeg, Manitoba, to a sample size of 15-20. All participants will be between the ages of 7 and 17, with unilateral upper limb differences. The upper extremity limb difference will be from any cause (congenital, trauma, secondary to other medical complications), and of any level (partial hand, wrist disarticulation, transradial, elbow disarticulation, transhumeral, shoulder disarticulation). Participants will be able to communicate in English and have the cognitive ability to follow instructions. Participants will live in Winnipeg or be willing to travel to RCC for two in person appointments (initial evaluation and final evaluation). Participants will be included regardless of history of prosthesis use.

Appropriate participants will be identified by their treating clinician (MG) and informed of the study. If they are interested in participating, they will sign a consent to contact for research form, and be contacted by another member of the research team (EH), who is not involved in their clinical care to review the consent form and ask any questions. Participants may also be recruited through self identification by sharing study information through posters at RCC, the RCC website and social media.

Data Collection: Each participant will provide informed consent before participating in any study related activities. At initial evaluation, each participant will complete a demographic questionnaire, as well as a semi-structured interview about their previous video game playing experiences, and their motivation to participate in playing video games in the future. The interviewing team member will record the interview on their phone and ensure that their phone is disconnected from the cloud. The recording will be transferred to the data storage system and then deleted from the phone. Anonymized data will be stored in a University of Manitoba Microsoft Teams environment. Following this interview, they will receive a training session from a team member (RG) on how to use the adapter and how to play Minecraft. This video game was chosen for its age appropriateness and need to use almost every button on the controller. Following the training, we will collect initial outcome measure data for both the with and without adapter conditions: time to complete the specified Minecraft “obstacle course”, accuracy of obstacle course (errors counted), VAS of satisfaction after playing, and the QUEST. Order of data collection with and without the device will be randomized to minimize a training effect.

Following the initial evaluation appointment, the participant will take home a tracking log, the video game controller adapter, and an Xbox with an Xbox One controller (if they do not already have one at home). Each participant will be asked to use the device daily and fill out the tracking log daily for 7 days. After which, each participant will return to RCC for the final evaluation appointment. At this time

the Minecraft “obstacle course” and evaluation will be repeated for gameplay with and without the adapter conditions. Finally, an exit semi-structured interview will be conducted to evaluate their experience with the adapter. Each participant will return the Xbox and controller if they were taken home. They will have the opportunity to keep the adapter if they wish.

Data Analysis: The semi structured interviews will be analyzed using an inductive coding approach as described by Thomas [7]. A transcript of the audio recorded interview will be created, formatted, and analyzed for any initial impressions and general tone. Codes will be assigned to the content of the interviews and then codes will be grouped into categories based on similarity of intent. The categories will then be refined and revised as each interview is added as a data source. A paired t-test will be used to analyze the performance measures and QUEST responses in order to determine if there was a clinically important difference between playing with and without the adapter. A repeated measures ANOVA analysis will be used to evaluate the VAS satisfaction scores, in order to determine if there was an increase in satisfaction with increased use of the adapter.

[figure not shown]
Knowledge Translation

We plan to address knowledge translation in several ways through this study. On an organizational level, we hope to share the results with the rest of the Rehabilitation Centre for Children (RCC) and Specialized Services for Children and Youth (SSCY) partners by presenting them at the monthly learning series, Breakfast at SCCY. We hope the findings of this study may translate to help additional populations seen at SSCY centre (i.e., hemiplegia/Cerebral Palsy). We also plan to share the results and adapter design with the War Amps CHAMP program, so that other children with upper limb differences across the country may benefit from the adaptation. To share our results with other health care providers, we plan to submit our results to be presented at the Association of Children’s Prosthetic Orthotic Clinics (ACPOC), Orthotics Prosthetics Canada (OPC), and RESNA Annual Conferences. Finally, we plan to write an article for a peer reviewed open-access journal to support broader knowledge translation.

Research Team

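### Run order is randomised because of a training effect, but the paired t-test ignores order and counts that effect as error

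*Protocol*

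**What the plan says.** In Research Methods, the Data Collection paragraph measures each child under both conditions and states: "Order of data collection with and without the device will be randomized to minimize a training effect". The performance outcomes are completion time and "accuracy of obstacle course (errors counted"). Before the first measured runs, each child is trained "on how to use the adapter and how to play Minecraft". Home use follows: "Each participant will be asked to use the device daily and fill out the tracking log daily for 7 days". At the final visit the course and "evaluation will be repeated for gameplay with and without the adapter conditions".

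The Data Analysis paragraph names the test: "A paired t-test will be used to analyze the performance measures and QUEST responses". Neither paragraph mentions an order or period term, or stratification by order. The protocol does not say whether the two orders will be balanced. The Participants & Sampling Technique paragraph sets recruitment "to a sample size of 15-20" and admits a wide range of children: "All participants will be between the ages of 7 and 17", with any level of limb difference.

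**The concern.** The design anticipates that the second run may go better than the first simply because it is second. Randomising the order stops this from favouring one condition on average, but it does not remove the effect from the data. A paired t-test reduces each child to one with-minus-without difference, so a practice gain pushes that difference up in one order and down in the other. The test cannot tell this spread from noise. The order is known for every child, so the spread can be removed.

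What is at stake is the standard error, the power and any interval reported from a small sample. The validity of the comparison is not in question.

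**Working it through.** **Inputs.** From the protocol: n = 15 to 20, two conditions per child, order randomised, paired t-test. The protocol gives no alpha, power, SD, true effect or size of training effect, so there is no figure of its own to reproduce. Assumed: two-sided 5% level, one visit at a time, and L and the true effect d both in SDs of the order-free paired difference, over a range of values.

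**Model.** Child i has difference y = d + L·s + e, with s = +1 or -1 by order and SD(e) = 1. The order groups have sizes n1 and n2.

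**Paired t-test.** The expected variance of the differences is 1 + L²·4·n1·n2/[n(n-1)]. For large balanced groups the SD factor is about √(1+L²): 1.03, 1.12 and 1.41 at L = 0.25, 0.5 and 1.0. The 95% half-width is t(n-1)·√(variance/n).
- n=15 (8:7), L=0.5: variance = 1 + 0.25·224/210 = 1.267; half-width = 2.145·√(1.267/15) = 0.623.
- n=20 (10:10), L=0.5: variance = 1 + 0.25·400/380 = 1.263; half-width = 2.093·√(1.263/20) = 0.526.

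**Order-adjusted estimate** (mean of the two order-group means): half-width = t(n-2)·½·√(1/n1 + 1/n2), whatever the value of L.
- n=15: 2.160·½·√(1/7 + 1/8) = 0.559.
- n=20: 2.101·½·√(1/10 + 1/10) = 0.470.

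The ratios at L=0.5 are 0.623/0.559 = 1.115 and 0.526/0.470 = 1.12. At L=0.25 the paired interval is 2-3% wider, and at L=1.0 it is 42-43% wider. In terms of sample size, n/(1+L²) at L=0.5 is 15/1.25 = 12 and 20/1.25 = 16.

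**Break-even.** Setting the two half-widths equal gives L = 0.13 (n=15) and 0.08 (n=20) with balanced orders. If orders come from simple randomisation, averaging over the possible splits gives 0.31 and 0.26.

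**Simulation** (100,000 trials per cell, balanced orders, values for n=15/n=20). Median half-widths run slightly below the formula values, which use the expected variance.

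| L | Paired t | Order-adjusted |
|---|---|---|
| 0 | 0.54/0.46 | 0.54/0.46 |
| 0.25 | 0.56/0.47 | 0.54/0.46 |
| 0.5 | 0.61/0.52 | 0.54/0.46 |
| 1.0 (extreme) | 0.78/0.66 | 0.54/0.46 |

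Power at L=0.5:

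| True effect | Paired t, balanced | Adjusted, balanced | Paired t, simple | Adjusted, simple |
|---|---|---|---|---|
| 0.5 SD | 35%/47% | 43%/56% | 36%/48% | 41%/54% |
| 0.7 SD | 62%/78% | 71%/84% | 61%/76% | 68%/82% |
| 1.0 SD | 91%/98% | 94%/99% | 90%/97% | 93%/98% |

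At L=0.25 with balanced orders the gain is at most about 2 points. Type I error of the adjusted test is 5% throughout. For the paired test with balanced orders it is 4.4%/4.3% at L=0.25 and 3.1%/2.9% at L=0.5, so the test is conservative. Neither estimate is biased on average.

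**The case against.** The strongest reply is that nothing here is wrong. Randomising order does what the protocol asks of it, the paired t-test is then valid, and choosing a more efficient valid test is close to preference. An unseen SAP could add an order term. The study is an exploratory case series that promises no confidence intervals. L is unknown and may be small: children are trained before the first run and asked for a week of home use before the last, and the wide mix of ages and limb levels may enlarge the SD by which L is scaled. For true effects of 1.0 SD or more, the power gain is about 1 to 3 points even at L=0.5.

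Most of this stands and limits the size of the point. It does not remove it, because the protocol itself names the test and itself expects a training effect. The widening applies to the t-test's standard error and power whether or not an interval is printed.

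Two technical objections also have force. With 10:10 orders the two estimates are identical, so the paired test loses power and reports too large a standard error, but the estimate is no noisier. And the protocol does not promise balanced orders: under simple randomisation the adjusted analysis is worth about 14 and 19 children at n=15 and n=20, and at L=0.25 it gains nothing. That is an argument for balancing the orders together with the adjustment; with both, 12 against 15 and 16 against 20 are the right comparisons.

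**Conclusion.** The concern holds as a low-cost gain in precision, not as an error of validity. The named test leaves any first-to-second-run gain in the error term, although the design records what is needed to take it out. With balanced orders and an assumed L of 0.5 SD, the interval is about 12% wider than necessary, and power is 6 to 10 points lower for true effects of 0.5 to 0.7 SD. At L=0.25 SD the loss is about 2 points or less. Below about 0.1 SD the paired t-test is no worse. Confidence in the size is medium, because neither L nor the true effect is in the protocol; the mechanism itself is algebra.

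**What to change.** Allocate the two orders in balanced blocks at each visit. For time and for errors, at each visit, regress each child's with-minus-without difference on order coded +1/-1, test the intercept on n-2 degrees of freedom, and report it with a 95% confidence interval. Using the same analysis for QUEST is optional, since a training effect is a less natural explanation for a satisfaction score.

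The cost is one analysis sentence, a balanced order list and one degree of freedom, with no extra data or visits. If there is no order effect, power falls by under 1 point with balanced orders. Without balancing it can fall by up to about 4 points, so the two changes should be made together.

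### A paired t-test is asked to establish a clinically important difference, but as described it can only show whether the mean difference is non-zero

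*Protocol*

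**What the plan says.** Under Research Methods, the Data Analysis paragraph states: "A paired t-test will be used to analyze the performance measures and QUEST responses". It gives the purpose as "in order to determine if there was a clinically important difference between playing with and without the adapter". The Data Collection paragraph lists the measures for each condition as course completion time, "accuracy of obstacle course (errors counted), VAS of satisfaction after playing, and the QUEST". The VAS is analysed separately by repeated measures ANOVA, so the t-test covers time, error count and QUEST.

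The Participants & Sampling Technique paragraph recruits by convenience "to a sample size of 15-20". Research Purpose sets an exploratory aim and describes the design: "This case series will use mixed quantitative and qualitative methods to compare performance and user satisfaction".

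Clinical importance is mentioned only as the purpose of the t-test. The protocol gives no non-zero null value for the test and no amount of time, errors or QUEST score against which importance would be judged.

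**The concern.** Whether a mean difference is zero and whether it is big enough to matter are separate questions. A paired t-test against zero answers the first. Its p-value depends on the number of children and the spread of the within-child differences as well as on the size of the benefit. A small benefit measured with little spread can be significant, and a worthwhile benefit measured with large spread can fail to be.

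The fault is the inference written into the sentence. That no threshold is given is not itself the complaint, since a statistical analysis plan could hold one.

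At stake is what the study may claim. Knowledge Translation plans conference submissions, a journal article, and sharing of the results and the adapter design with a program for children with limb differences. A statement about clinical importance that rests on a p-value would travel with them.

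**Working it through.** The protocol states no alpha, SD, effect size, power or dropout, so there is no figure of its own to reproduce. What follows is an illustration.

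**Inputs**
- From the protocol: paired comparison; n = 15 to 20.
- Assumed: two-sided alpha 0.05, no dropout, roughly normal differences. Effects are in units of the SD of the within-child differences.

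**1. Same observed benefit, different n.** With an observed mean difference of 0.5 SD, t = 0.5 × √n on n − 1 degrees of freedom.

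| n | t | p |
|---|---|---|
| 15 | 1.94 | 0.073 |
| 16 | 2.00 | 0.064 |
| 17 | 2.06 | 0.056 |
| 18 | 2.12 | 0.049 |
| 19 | 2.18 | 0.043 |
| 20 | 2.24 | 0.038 |

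The result crosses 0.05 between 17 and 18 children, while the benefit is unchanged.

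**2. Where the cut-off lies.** The smallest observed difference that reaches significance is t(0.975, n − 1)/√n. This is also the half-width of the 95% CI.
- n = 15: 2.145/√15 = 0.55 SD. An observed 0.5 SD has 95% CI 0.5 ± 0.55, or −0.05 to 1.05 SD.
- n = 20: 2.093/√20 = 0.47 SD. The 95% CI is 0.5 ± 0.47, or 0.03 to 0.97 SD.

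With other assumed alphas the cut-offs at n = 15 and n = 20 are 0.45 and 0.39 SD (alpha 0.10), or 0.77 and 0.64 SD (alpha 0.01). They are fixed by alpha, n and the SD. Nothing in the formula refers to an amount of time, errors or QUEST score that matters to a child.

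**3. Non-significant results at a real difference.** If the true difference is 0.5 SD, the noncentral t distribution gives a non-significant result in 56.2% of studies with n = 15 and 43.5% with n = 20. Simulation of 400,000 studies gave 56.1% and 43.4%. The 0.5 SD is illustrative and is not claimed to be the important difference.

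**4. Error in both directions.** Let D be an important difference of unspecified size.
- True difference half of D, SD = 0.5 D: the standardised difference is 0.5/0.5 = 1.0. The test is significant with probability 0.95 (n = 15) or 0.99 (n = 20), although the true benefit is only half the important one.
- True difference equal to D, SD = 1.5 D: the standardised difference is 1/1.5 = 0.67. The test is significant with probability 0.67 or 0.81, so it misses an important benefit with probability 0.33 or 0.19.

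**The case against.** The strongest reply is that this is one loose phrase with no decision attached. The protocol states no alpha, success criterion or rule that significance will be declared importance. The t-test may simply be the tool for the comparison, with importance judged from the mean difference and CI that usually accompany it. A paired t-test can also be run against a non-zero null, and a statistical analysis plan not seen here could supply that value or a threshold. The figures above rest on assumed inputs and would apply to any zero-null test of this size. Finally, the study is exploratory, and interviews and the VAS also bear on whether the adapter helps.

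Part of this stands. The numbers are generic illustrations, no formal decision hangs on the p-value, and the other evidence limits the harm. The main point survives. The sentence names the paired t-test as the means of determining clinical importance, and nothing in it suggests a non-zero null. If statistical significance was meant, the wording is wrong. If importance was meant, the method described does not deliver it. A threshold held elsewhere would leave the protocol sentence needing correction, because no threshold enters the test it describes.

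**Conclusion.** The concern holds. The protocol assigns the paired t-test a conclusion that the test, as described, cannot give. This should be fixed, though the likely harm is modest: a risk of misreading three comparisons (time, errors, QUEST) in a small exploratory case series. The logical point needs no numerical assumption. Its illustrated size, with an observed 0.5 SD difference falling on either side of 0.05 within 15 to 20 children, depends on the assumed alpha, complete data and approximate normality.

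**What to change.** Reword the sentence in Data Analysis so that the paired t-test addresses only whether the mean difference between conditions in completion time, error count and QUEST differs from zero. Report each mean paired difference with its 95% CI.

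Then choose one of two courses:
- remove the reference to clinical importance; or
- keep it, and before results are seen specify and justify a smallest worthwhile difference for each measure, then interpret the estimate and CI against it.

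The cost is one reworded sentence and the reporting of intervals. Thresholds need agreement only under the second course. No change to recruitment or data collection is needed. The downside is that some results will have to be reported as inconclusive about importance.

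### The repeated measures ANOVA named for the VAS would, in its classical form, discard a non-returning child's two first-visit scores; a mixed model keeps them, for a small and conditional gain

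*Protocol*

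**What the plan says.** The Data Analysis paragraph of the protocol names one method for the VAS: "A repeated measures ANOVA analysis will be used to evaluate the VAS satisfaction scores". Its purpose is given as "in order to determine if there was an increase in satisfaction with increased use of the adapter", so it has to compare the first and final visits.

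The Data Collection paragraph supplies the scores. At the first visit, "we will collect initial outcome measure data for both the with and without adapter conditions", and the VAS is among those measures. After a week at home ("Each participant will be asked to use the device daily and fill out the tracking log daily for 7 days"), "each participant will return to RCC for the final evaluation appointment", where the "evaluation will be repeated for gameplay with and without the adapter conditions". That makes 2 visits × 2 conditions = 4 planned VAS scores per child.

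The Participants & Sampling Technique paragraph recruits "to a sample size of 15-20" and asks families living outside Winnipeg to be "willing to travel to RCC for two in person appointments (initial evaluation and final evaluation"). The protocol gives no expected loss and does not say what happens to the scores of a child who does not come back.

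**The concern.** Classical repeated measures ANOVA works on children with every cell filled. A child seen once therefore contributes nothing to the VAS analysis, although both first-visit scores are in hand. If children who rated the adapter low at the first visit are less likely to return, the children who remain start from a higher first-visit mean. The estimated gain is then too small and the final adapter rating too high. With 15-20 children, each one lost counts.

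This concerns a method that the protocol states, and a replacement of equal simplicity is available.

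**Working it through.** The protocol gives no power, SD, effect size or loss rate, so there is no planned figure to reproduce. Every input below other than the sample size and the four-score layout is an assumption.

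**1. Does the named method drop children?** One data set was simulated with 18 children, 3 of them without a final visit. Observed scores: 18 × 4 − 3 × 2 = 66. A standard repeated measures ANOVA routine rejected these data as unbalanced. It ran only after the 3 children were removed, on 15 × 4 = 60 scores (error df 14). A mixed model used all 66.

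**2. How likely is any loss?** P(at least one lost) = 1 − (1 − p)^n.

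| Assumed p | n = 15 | n = 20 |
|---|---|---|
| 5% | 54% | 64% |
| 10% | 79% | 88% |
| 20% | 96% | 99% |

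**3. Random loss.** Neither method is biased. The mixed model lowers the RMSE of the change by about 0-3%.

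**4. Loss depending on the first-visit adapter score.** Let d be the amount, in SD units, by which returners' first-visit mean exceeds that of all children, and r the correlation between visits. For complete cases:
- bias of the final mean = r·d
- bias of the change = r·d − d = −(1 − r)·d

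Assume 3 of 15 or 4 of 20 lost, with selection weight exp(−1.5·z), z being the standardised first score. Then d is about 0.24:

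| r | Final mean, r·d | Change, −(1 − r)·d | Simulated change (n = 15 / 20) |
|---|---|---|---|
| 0.3 | +0.07 | −0.17 | −0.164 / −0.173 |
| 0.5 | +0.12 | −0.12 | −0.117 / −0.118 |
| 0.7 | +0.17 | −0.07 | −0.068 / −0.072 |

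A likelihood analysis of all scores stayed within 0.005 SD of zero. RMSE for the change, complete-case against likelihood, was 0.368 vs 0.334 (n = 15, r = 0.3), 0.341 vs 0.296 (n = 20, r = 0.3) and 0.232 vs 0.229 (n = 15, r = 0.7), which is 1-13% lower.

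With one child lost and the milder weight exp(−0.5·z), the complete-case bias is at most 0.02 SD and the RMSEs differ by about 1% or less. With 2 of 20 lost it is 0.015-0.04 SD, and the RMSEs differ by 0-3%.

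A second simulation used all four scores, SD 20, a true gain of 10 points and a logistic loss model (log-odds 1 per SD, nominal 20% loss). Complete cases gave a gain of 7.0-8.9 points; the likelihood fit, with covariance taken as known, gave 9.9-10.1. The largest bias, 3.0/20 = 0.15 SD, agrees with the table.

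**5. Loss depending on the final score.** This represents dislike that forms at home. Let d now be the shift in returners' final mean. Then:
- complete-case bias of the change = d − r·d = (1 − r)·d
- likelihood bias of the change ≈ (1 − r²)·d, because the first-visit mean is recovered but the final mean only partly, with a regression slope of about r

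The likelihood bias is larger by a factor of about 1 + r. With the weight of 1.5 and the 20% loss of step 4:

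| r | Complete-case change bias | Likelihood change bias |
|---|---|---|
| 0.3 | +0.17 to +0.18 | +0.22 to +0.23 |
| 0.5 | +0.12 | +0.19 |
| 0.7 | +0.07 | +0.13 to +0.14 |

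The likelihood RMSE was also higher, for example 0.311 vs 0.280 (n = 20, r = 0.5). For the final level alone the order reverses: about (1 − r²)·d for the likelihood analysis against d for complete cases.

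**The case against.** **Territory of the SAP.** The protocol only names a family of tests; complete-case deletion is inferred from the name, and missing-data rules usually sit in an SAP, which is not at hand. This stands as a limit: the point applies to the classical form of the method. It is still a comment on a stated choice and does not complain of missing detail.

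**No evidence of loss.** Follow-up is one visit after 7 days, families agree to both visits beforehand, and borrowed equipment is handed back at the second. Losses may be few or none. The 20% loss is assumed, and the weight of 1.5 makes a child 1 SD below the mean about 20 times (e³) as likely to be lost as one 1 SD above. This stands, and it is why 0.17 SD is the top of a range.

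**The remedy may not fit the cause.** A child put off by the week at home is lost because of something that the first-visit score does not show. Step 5 of the working confirms that the mixed model then does worse for the change. This stands in full and rules out calling the ANOVA simply the inferior method.

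**Stronger readings that the documents do not support.** A reader might infer that satisfaction as a whole is judged on returners only. It is not: QUEST is collected with and without the adapter at the first visit and has its own paired t-test, and the interviews are analysed separately. A reader might also infer that the ANOVA would manufacture a gain in satisfaction. When loss follows a low first score, the complete-case gain is understated.

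**Conclusion.** The point holds in a limited form. In its classical version the named ANOVA discards first-visit VAS scores that a mixed model would use, and with complete data the two agree. If a few children are lost, the mixed model offers about 0-3% lower RMSE for the change under random loss, and it removes a bias of roughly 0.02 to 0.17 SD if loss depends on the first-visit score. Even the upper figure is smaller than the sampling error: RMSE was 0.23-0.37 SD in the settings listed in step 4.

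The advantage for the change rests on loss being random or explained by observed scores, which cannot be verified in this study. If loss follows dislike formed at home, the mixed model's change estimate can be the more biased one, although its final-level estimate is the less biased. In an exploratory case series with convenience sampling and no power claim, this is an optional, inexpensive improvement to the VAS analysis alone.

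**What to change.** In Data Analysis, replace the repeated measures ANOVA with a linear mixed model on all observed VAS scores: fixed effects for condition, visit and condition-by-visit, a stated within-child correlation structure across the four scores, REML estimation and Kenward-Roger degrees of freedom. State that it assumes loss is explained by the observed scores. Report how many children did not return and their first-visit scores, and give the complete-case change beside the model estimate as a sensitivity analysis. If the two differ, the text should say that the data cannot show which is nearer the truth.

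The cost is two or three sentences and standard software, with no new data or visits and nothing lost if every child returns. The downside is reliance on the missing-at-random assumption, which the sensitivity analysis makes visible.
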